Title: Impact of dark chocolate consumption on glucose levels of people with diabetes

Research Question: Does dark impact blood glucose levels in people with diabetes?

Objectives

- 1) To determine whether a dark chocolate sweetened with stevia, erythritol, and inulin compared to a standard dark chocolate bar impacts blood glucose levels in individuals with diabetes (T1D and T2D);
- 2) to understand and manage glucose levels in people with diabetes after consumption of different blends of chocolate.

Hypothesis:

a) A dark chocolate sweetened with stevia, erythritol, and inulin, compared to a standard dark chocolate bar will not impact blood glucose levels in individuals with diabetes (T1D and T2D)

Background Information

Diabetes is a growing concern in the world with an estimated 9.3% of adults, ages 20-79, with it in 2019, type 2 diabetes accounting for 90% of this total (1). In Canada, approximately 7.5% of adults have type 2 diabetes, 4.7% diagnosed and 2.8% undetected (2). Furthermore, an estimated 12.4% of adults in Canada have prediabetes, with 5-10% of those becoming diabetic each year (2). In order to prevent this, interventions aimed at weight loss, dietary change, and increased physical activity have been found to be effective (3). Additionally, a common recommendation for individuals with type 2 diabetes is to limit sugars and sweets as it may cause a high blood glucose response (4).

In diabetes, the postprandial phase is characterized by a rapid and large increase in blood glucose levels, and the possibility that these postprandial "hyperglycemic spikes" may be relevant to the pathophysiology of late diabetes complications is recently receiving much attention (5).

Postprandial hyperglycemia is a major component of glucose toxicity at the cellular and tissue level. Acute elevations of glucose after nutrient ingestion are associated with a variety of glucose-mediated tissue defects, including oxidative stress, lipid peroxidation, and advanced glycation end products (AGEs) formation leading to endothelial dysfunction and inflammation (6). This state not only initiates the development of early microvascular and macrovascular complications, but it also can contribute to a rapid progression to diabetes by causing glucose toxicity in muscle and pancreatic beta cells. The effects of hyperglycemia are often irreversible and lead to cell dysfunction.

Therefore, strategies aiming at the specific reduction of postprandial hyperglycemia must be utilized to minimize clinical damages (7).

Chocolate is often avoided due to the sugar content, however, high-polyphenol chocolate has a beneficial effect on hyperglycaemia. (8) In a study looking at consumption of isocaloric doses of dark, milk, and white chocolate, blood glucose levels were higher 30 minutes after ingestion of the white and milk chocolate compared to the dark chocolate (9). This offers potential for individuals with diabetes to consume chocolate products depending on sugar and cocoa content. Daily consumption of flavonoid-rich chocolate have shown improved fasting plasma glucose levels and insulin resistance, three times greater than in milk chocolate (10). It has also been shown that a 15-day administration of polyphenolrich dark chocolate decreased blood pressure and increased insulin sensitivity in healthy subjects (11). Similar results after 4-week consumption of polyphenol-rich dark chocolate; improved fasting glucose and decreased insulin resistance (12). By consuming high-quality cocoa products such as dark chocolate, insulin function could be improved, blood sugar better controlled, and possibly, the incidence of prediabetes is lowered (13). Therefore, it appears that the health benefits from chocolate are predominantly from the dark chocolate form.

The sugar-free chocolate from Ross Chocolates is formulated with a blend of inulin, erythritol, and stevia. These alternatives to sugar are not expected to cause a significant change in blood glucose levels following consumption. A study evaluating the consumption of sucrose, fructose, and isomalt-sweetened chocolates in type 2 diabetes patients found that while the sucrose and fructose-sweetened chocolates induced a similar glycemic effect, the isomalt-sweetened chocolate produced a lower glycemic effect (14). Therefore, since it has never been tested scientifically before, it would be novel and beneficial to assess if Ross Chocolates' blend of sweeteners would lead to a lower or null glucose spike in people with diabetes. Confirmation of this key piece of evidence could open the door for longer term studies easing concern over sugar-free dark chocolate postprandial hyperglycemia.

Research Method

Twenty (N=20) individuals at University of British Columbia with physician diagnosed T1D (N=10) or T2D (N=10) (HbA1c 6.5-8.5%), between the ages of 18-75 years, with a BMI between 25-40 kg/m² will be recruited through online social media and newspaper advertising.

Inclusion criteria will be: i) physician-diagnosed T1D or T2D of ≥1 year; ii) current HbA1c of 6.5-8.5%; iii) BMI: 25-40 kg/m2; iv) blood pressure of <160/99 mm Hg assessed according to guidelines; v) non-smoking; vi) not on hormone

replacement therapy, corticosteroids, or anti-inflammatory medications; and vii) 18–75 years old. **Exclusion criteria will include** i) Are taking more than 2 glucose lowering medications; ii) Are ongoing medical treatment for diseases such as cancer, auto-immune or inflammatory disease, liver or kidney disorders; iii) Have allergy, intolerance or aversion to cocoa, stevia, erythritol, inulin, or any other dietary restrictions (e.g., vegan) that will prevent them from following the standardized study diets; iv) Are unable to follow remote guidance by internet or smartphone; v) Are unable to follow the controlled diet instructions; vi) Are unable to read or communicate in English.

Based on our previous studies ~55% of males and ~70% of females with T1D or T2D who volunteer will meet these eligibility criteria so we anticipate no recruitment issues. We will allow statins and anti-hypertensive medications if on a stable dose for 3 months because the majority of T2D patients are on at least one of these medications; excluding them would leave a small pool for recruitment and limit the generalizability of our findings. Interested participants will provide their e-mail to establish direct and individual communication with research team.

A double-blinded crossover pilot trial is proposed. Eligible participants will complete 2 experimental trials separated by approximately 2-7 days, consuming no-sugar dark chocolate from Ross Chocolates and a conventional dark chocolate bar.

Due to COVID-19 breakout, this study is proposed to be done remotely since participants belong to risk group and will probably maintain in quarantine for unpredictable time. Information and guidance for the trial will be done by email, telephone calls and Zoom meeting. RedCap-UBC will be used to manage information and deliver questionnaires. Participants will be recruited after completing an online Eligibility questionnaire.

Participants will receive in their homes a box containing a OneTouch Verio IQ® kit Blood glucose monitoring system (OneTouch Verio IQ® meter, lancing device, sterile lancets, carrying case), glucose strips, alcohol swabs, 1 bar of Ross dark chocolate (34g each) and 1 bar of a conventional dark chocolate (34g each) and instructions on how to proceed during each trial. Chocolate bars will be identical and wrapped equally and labeled as A and B, by Ross Chocolates (prepared in the same mold and packaged identically) who are not involved in any other aspects of the study, allowing for blinding of research team and participants. Participants will complete two experimental trials: 1) consumption of 1 bar (34g) of Ross dark chocolate 2) consumption of 1 bar (34g) of conventional dark chocolate. The order of the bars will be randomized so there will be an equal chance of getting bar A or bar B first (similar to drawing a name out of a hat or flipping a coin). Participants will be advised to perform both trials on the exact same time of day, in the morning after an overnight fast, refraining from diabetic medications. They will be asked to register glucose levels before and after eating the chocolates. A OneTouch Verio

IQ® meter will be used to measure blood glucose. Time points will be as follows: before consumption, 15 min after, 30min after, 45min after, 60min after, 90min after, 120min after. Values will be registered on a Glucose Form and stored on the meter and sent to research team by email. Participants will then be asked to Complete Taste Test Questionnaire sent by RedCap link through e-mail.

Study Timeline:

Baseline Contact

On the initial contact, by a FIRST email, participants will be informed of the study and asked to complete a Health Screening Questionnaire and sign electronically an Informed Consent. After confirmation of eligibility and given consent, participants will receive a SECOND email with information on the study kit and asked to inform Research team when kit arrives. The kit will contain:

- Study Welcoming, Instructions and Responsibilities
- Glucose levels form
- OneTouch Verio IQ® kit Blood glucose monitoring system (OneTouch Verio IQ® meter, lancing device, sterile lancets, carrying case)
- Glucose strips
- Alcohol swabs
- 1 bar of dark chocolate A (34g each)
- 1 bar of dark chocolate B (34g each)

Once participants confirm study kit was received, they will get a THIRD email suggesting to start the protocol.

Participants will choose 2 different days, one for Day 1 and one for Day 2 (2-7 days apart from each other) and perform the following protocol:

Day 1

- ✓ Measure glucose levels before chocolate consumption and write down value on Glucose levels form
- ✓ Consume 1 bar of dark chocolate (A or B) according to instructions from Research team after randomization

- ✓ Measure glucose levels after consumption (15 min, 30 min, 45 min, 60 min, 90 min, 120 min) and write down values on Glucose levels form
- ✓ Complete Taste Test Questionnaire sent to participant's e-mail

Day 2

- ✓ Measure glucose levels before chocolate consumption and write down value on Glucose levels form
- ✓ Consume 1 bar of dark chocolate (A or B) according to instructions from Research team after randomization
- ✓ Measure glucose levels after consumption (15 min, 30 min, 45 min, 60 min, 90 min, 120 min) and write down values on Glucose levels form
- ✓ Complete Taste Test Questionnaire sent to participant's e-mail
- ✓ Send photo of Glucose levels form by email

A Zoom meeting will be scheduled to guide participants with procedures in study if necessary.

Statistical Analysis

Changes in blood glucose across time between conditions will be analyzed with a linear mixed effects model including time, condition, and their interaction as fixed effects and participant ID and baseline glucose values as random effects. Area under the curve and incremental AUC will be calculated and analyzed by paired t-test.

Sample size

Sample size calculation for a within-between interaction with alpha of 0.05, power of 80%, and an expected moderate effect size (f=0.25) reveals a sample size of 12 is needed to detect a significant difference. To preserve power and enable potential sub-analyses of type 1 vs. type 2 diabetes we will aim to recruit 20 participants for this preliminary study.

Significance

The results of this study will help determine whether by consuming a dark chocolate bar sweetened with stevia, erythritol, and inulin will cause a blood glucose spike in people with diabetes (T1D and T2D). This information will provide high quality scientific evidence which will allow individuals with diabetes more food choices, helping them manage diabetes better.

OUTCOMES MEASUREMENTS AND METHODS

The primary outcome measure is plasma glucose levels following consumption of the dark chocolate bars. The taste of the chocolates will also be evaluated.

Glucose Monitoring

A glucose monitoring device (OneTouch Verio IQ® kit Blood glucose monitoring system) will be used to measure blood glucose levels before and after consumption of chocolates. Following consumption, measurements will be taken 15 min after, 30 min after, 45 min after, 60 min after, 90 min after, and 120 min after. Values will be registered on a form, stored on the meter and sent to research team by email. All to be done at home with no displacement.

Taste Test Questionnaire

Questionnaire is included as attachments and will be sent as link from the RedCap platform.

Protection of Human Subjects

All participants will be given a unique study code, with all data and information gathered connected with this code. Only the PI will have access to the master list linking the codes with participant names. Participant information and data will be either stored in a locked filing cabinet, or on an internal UBC network drive accessed only through a dedicated LAN internet connection on a password protected computer in the PIs laboratory with Salto passcard access only to the members of the research lab.

REDCap will be used as project management, storage of information, sending questionnaires and processing results. The REDCap platform is a secure web application for building and managing research data collection instruments. The platform is specifically designed to support online or offline data capture for research studies. The REDCap platform runs on server infrastructure physically located in BC, Canada, at the UBC University Data Centre (UDC).

POTENTIAL PROBLEMS AND ALTERNATIVE STRATEGIES

Diet compliance: Since the study involves a minor modification to diet, we do not anticipate that any adverse events due to the interventions will be seen.

Blood sampling:

When compared to traditional wet blood and plasma collection using venipuncture, capillary blood sampling is safer and easier, so much so that nearly anyone can perform the procedure, mainly diabetes patients who are used to doing finger pricks for glucose levels. However, risks associated with the process of finger-stick blood draws are minimized by usage of sterile and disposable material as well as hygiene procedures. Participants will receive their own kit with sterile material and instructions on procedure.

Protection of personal data: All participants will be given a unique study code, with all data and information gathered connected with this code. Only the PI will have access to the master list linking the codes with participant names. Participant information and data will be either stored in a locked filing cabernet, or on an

internal UBC network drive accessed only through a dedicated LAN internet connection on a password protected computer in the PIs laboratory with Salto passcard access only to the members of the research lab.

REDCap will be used as project management, storage of information, sending questionnaires and processing results. The REDCap platform is a secure web application for building and managing research data collection instruments. The platform is specifically designed to support online or offline data capture for research studies. The REDCap platform runs on server infrastructure physically located in BC, Canada, at the UBC University Data Centre (UDC).

Informed consent and ethics: Prior to beginning the study Informed consent will be obtained from participants and they will be informed they can withdraw at any time. They will be informed that this study is partially funded by Ross Chocolates through a Mitacs Accelerate Grant. Ross Chocolates is a for-profit company that may stand to benefit commercially from research on how its sugar-free chocolate impacts blood sugar levels.

References

(2) Hosseini, Zeinab, et al. "Type 2 diabetes prevalence among Canadian adults--dietary habits and sociodemographic risk factors." Applied Physiology, Nutrition, and Metabolism, vol. 44, no. 10, 2019, p. 1099+. Gale OneFile: Health and Medicine, https://link-gale

com.ezproxy.library.ubc.ca/apps/doc/A603404292/HRCA?u=ubcolumbia&sid=HRCA&xid=f24562d2. Accessed 9 June 2020.

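### The hypothesis is that the sugar-free bar has no impact on glucose, but no contrast, interval or limit is pre-specified by which any planned result could support no impact or no spike

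*Combined protocol and SAP*

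**What the plan says.** Two kinds of claim appear in the combined protocol and SAP.

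- **Comparative.** Objective 1 asks about the test bar relative to a standard dark chocolate bar. The Background includes a lower spike among the outcomes of interest.
- **Absolute.** The Hypothesis is that the test bar "compared to a standard dark chocolate bar will not impact blood glucose levels in individuals with diabetes (T1D and T2D". The Background says the sweeteners "are not expected to cause a significant change in blood glucose levels following consumption" and asks whether the blend "would lead to a lower or null glucose spike in people with diabetes". The Significance section says the results will help settle whether the test bar produces a spike.

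The analysis is stated in two sentences. The first gives a "linear mixed effects model including time, condition, and their interaction as fixed effects", for glucose changes over time between conditions. The second says "Area under the curve and incremental AUC will be calculated and analyzed by paired t-test". The Sample size section gives 12 as the number needed to find a difference and aims for 20. The Research Method splits these into 10 with each type of diabetes.

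On status, the Research Method says "A double-blinded crossover pilot trial is proposed" and the Sample size section calls the study preliminary. The Background adds: "Confirmation of this key piece of evidence could open the door for longer term studies".

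**The concern.** A lower response and a null response need different evidence. The first is a between-bar difference, which the plan tests. The second concerns the size of the test bar's own rise, and needs an estimate of that rise, an interval, and a statement of how large a rise would still count as none. The plan supplies none of these.

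The hypothesis is also ambiguous. Read literally as no difference between bars, it would be contradicted by a significant benefit of the test bar, which is the result the Background hopes for. Read as no rise, unlike the standard bar, it has no planned contrast. On neither reading does a pre-stated result support it.

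At stake is the no-spike half of the question. Any conclusion there would rest on a criterion chosen after the data are seen, although the plan expects the results to inform longer studies and food choices.

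**Working it through.** **1. The plan's own figure.** Inputs from the Sample size section: f = 0.25, alpha 0.05, power 80%, within-between interaction, N = 12. The number of groups k, measurements m, correlation ρ and sphericity are not given. I assume k = 2, m = 14 (two bars × seven readings), ρ = 0.5 and sphericity.

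- λ = f²·N·m/(1 − ρ) = 0.0625 × 12 × 14/0.5 = 21
- df1 = (k − 1)(m − 1) = 13; df2 = (N − k)(m − 1) = 10 × 13 = 130
- Power = 83.8%

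So 12 can be reproduced, though other settings give other answers (m = 7 with ρ = 0.5 gives 18). It sizes a test for a difference, and the present point does not depend on it.

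**2. Claims set against planned analyses.**

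| Claim | Evidence needed | In the plan? |
|---|---|---|
| Lower than the conventional bar | Between-bar comparison | Yes: interaction term, paired t-tests |
| No difference between bars | Equivalence limit and interval | No |
| No rise or spike after the test bar | Test-bar change from fasting, interval, limit | No; estimable from the model, but not named |

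**3. What non-significance would show.** No SD is given, so effects are in units of the SD of the within-person quantity (between-bar difference, or test-bar change from fasting). Miss rate = P(|t| < t crit) under a noncentral t with df = n − 1 and noncentrality d√n, two-sided 0.05. For d = 0.5:

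- n = 20: noncentrality 0.5 × √20 = 2.236, critical value 2.093, miss rate 43.5%
- n = 10: noncentrality 0.5 × √10 = 1.581, critical value 2.262, miss rate 70.7%

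| True effect | n = 20 | n = 10 |
|---|---|---|
| 0.3 SD | 75% | 86% |
| 0.5 SD | 44% | 71% |
| 0.8 SD | 8% | 38% |

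The 95% CI half-width is 2.093/√20 = 0.47 SD at n = 20 and 2.262/√10 = 0.72 SD at n = 10. Effects of half an SD or more are therefore compatible with many non-significant results.

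**4. What a workable criterion would cost.** These are simulations with normal changes and equal between-time correlations of 0.3 to 0.8, in single-time SD units. With zero true change, the chance that the upper 95% limits at all six times lie below the limit is:

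| Limit | n = 20 | n = 10 |
|---|---|---|
| 0.5 SD | 11–33% | 1–10% |
| 0.8 SD | 69–82% | 14–37% |

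A signed average over 0–120 min passes more easily but does not address a spike. The trapezoid weight at each of 15, 30 and 45 min is 15/120 = 0.125. A true rise of 0.5, 1.0 and 0.5 SD at those times therefore enters the average as 0.125 × (0.5 + 1.0 + 0.5) = 0.25 SD. At n = 20 the average then still passes a 0.8 SD limit in 78–97% of trials and a 0.5 SD limit in 24–41%, although the peak exceeds both. Under the six-time rule, the 30-minute reading alone would hold that false pass to at most 2.5%.

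**The case against.** The strongest defence is that Objective 1 is comparative, that the planned tests match it, and that the between-bar contrast is the only randomised one. The trial is labelled a pilot. The model can estimate the test bar's own change. Participants are tested "in the morning after an overnight fast, refraining from diabetic medications" with no no-food condition, so even a well-specified change from fasting cannot isolate the effect of the bar. On this view only the wording needs attention.

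Much of that stands. The between-bar comparison is valid, and most of the remedy is rewording. But being able to estimate a quantity is not the same as naming it: with six post-consumption times and several possible summaries, the choice stays open until the data are in. The pilot label limits what may be claimed, but does not supply the missing criterion for the stated hypothesis.

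A reader might infer three stronger points that the documents do not support:

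- **That every planned test is between bars.** The model has a time term, which tests change pooled over both bars. It gives neither a test-bar contrast nor a limit, but it is not a between-bar test.
- **That the investigators will read a non-significant p-value as no impact.** Nothing says so. The miss rates show only why that reading must be ruled out.
- **That incremental AUC will be compared with zero.** Only a paired test is planned. The plan does not say how readings below fasting enter the incremental AUC, but that is a separate and minor gap in definition.

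**Conclusion.** The point holds and should be fixed. It is a mismatch between hypothesis and analysis: the plan can support a lower response than the conventional bar, but no planned result can support no impact or no spike. It does not invalidate the trial or the between-bar comparison.

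The absence of a test-bar contrast, interval and limit is read directly from the text and needs no assumption. The figures in the working do rest on assumptions: SD units, because no SD is given, and for the simulations also normal changes and the stated correlations. They show how little non-significance would establish at 20 participants, and less at 10. They do not measure harm to the planned comparison.

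**What to change.** 1. Restate the hypothesis as a lower glucose response after the test bar than after the conventional bar. Test it with the planned two-sided comparison and report the estimate with its 95% CI.
2. Report the test bar's change from fasting at each of the six times, with 95% CIs from the planned model, as estimation. Claim no meaningful rise or no spike only under a peak-sensitive criterion, for example all six upper 95% limits below a limit that the investigators justify. Fix the criterion before any outcome data are reviewed, even by A/B label. Waiting until unblinding is too late, because curves by label can be seen before then. Do not use the 0–120 min average for this claim.
3. State that a non-significant p-value will not be read as no effect.
4. State that, without a no-food condition, change from fasting cannot separate the bar's effect from background drift.

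This needs no new data and no change of design. The cost is that a no-spike claim becomes hard to make, as the six-time pass rates show. The trial may end up supporting only a lower response, together with the test-bar estimates.

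### The medication hold for the fasted home sessions is one rule for T1D and T2D, and the protocol text gives no drug scope, last-dose or resumption time, or glucose action value

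*Combined protocol and SAP*

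**What the plan says.** Research Method plans twenty participants, ten with T1D and ten with T2D. Each eats one masked bar on each of two mornings. The sessions take place "in the morning after an overnight fast, refraining from diabetic medications". No other sentence in the document deals with withholding treatment.

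The only entry limit on glucose-lowering treatment is the exclusion "Are taking more than 2 glucose lowering medications". Insulin is neither named nor excluded.

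Glucose Monitoring describes the setting: "All to be done at home with no displacement". Seven readings are taken, one before the bar and six up to 120 minutes after it. The Day 1 and Day 2 checklists under Study Timeline ask the participant to measure, write the value down, eat the bar and measure again. They do not repeat the hold, and they attach no action to any glucose value. "Send photo of Glucose levels form by email" is on the Day 2 list only.

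Support is remote: "Information and guidance for the trial will be done by email, telephone calls and Zoom meeting". The kit also contains "instructions on how to proceed during each trial", whose content is not reproduced.

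Under Potential Problems and Alternative Strategies, the diet-compliance paragraph expects no adverse events from the interventions because the dietary change is small. The blood-sampling paragraph deals with finger-stick risk. Neither mentions withheld treatment.

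**The concern.** The hold is a second thing the trial does to participants, separate from the bar. For someone with T2D on one or two tablets, delaying a morning dose may matter little. For someone with T1D, the same words can be taken to cover insulin that should not be omitted without advice. The protocol leaves each participant to decide how far the hold reaches, then has that person eat a masked bar, which on one of the two days is the conventional one, alone at home and with no written value at which to act.

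What is at stake is participant safety. The result is affected only secondarily, and mainly through the remedy: once stopping values exist, the analysis needs a rule for sessions that are stopped.

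**Working it through.** The plan states no figure on this point, so there is none to reproduce. The check sets the relevant sections side by side, followed by a short calculation of what the remedy costs.

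**1. Who is under the hold.** 10 of 20 planned participants have T1D: 10/20 = 50%. Each eats the conventional bar once, so there are 10 planned T1D sessions with that bar.

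**2. Does any criterion keep insulin users out?** No. The exclusion starts above two glucose-lowering medications. Basal plus mealtime insulin counts as two and does not exceed it.

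**3. What the text specifies about the hold.**

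| Item | In the protocol text? |
|---|---|
| Link to the morning fasted session | Yes |
| Which drugs or insulin components are held | No |
| Separate instructions for T1D and T2D | No |
| Time of last dose | No |
| Time treatment resumes | No |
| Glucose value for not starting, stopping, treating or calling | No |
| The hold considered in the risk text | No |

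**4. How far the words reach.** Insulin is a diabetes medication, so the literal scope includes basal and pump insulin. On the narrower reading, a hold for the morning session only, basal insulin is missed if it is due that morning or delivered by pump. The documents give no insulin regimens, so the number affected cannot be counted.

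**5. What stopping does to the analysis.** Statistical Analysis says "Area under the curve and incremental AUC will be calculated and analyzed by paired t-test". A session stopped early has no complete 120-minute curve, so its pair would drop out of those tests. If stops follow high readings, they may be more frequent after the conventional bar. The lost pairs would then tend to be those with the largest difference between bars, and the mean paired difference would shrink toward zero. That is the direction of the stated hypothesis of no impact. The mixed model in the same section can use readings taken before a stop, so those readings, including the one that triggered the stop, should be kept.

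**6. Precision cost of lost pairs.** Paired t-test, two-sided alpha 0.05, power 80%, noncentral t with n − 1 degrees of freedom and noncentrality d√n, where d is the mean paired difference divided by the SD of the differences. Solving for d:

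| Pairs | Pairs lost | d | Ratio to 20 pairs |
|---|---|---|---|
| 20 | 0 | 0.660 | 1.00 |
| 19 | 1 (5%) | 0.680 | 1.03 |
| 18 | 2 (10%) | 0.701 | 1.06 |
| 17 | 3 (15%) | 0.724 | 1.10 |

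The loss of 1 to 3 pairs is an assumption. The table covers the smaller n only. It does not cover the bias in step 5.

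**The case against.** The best defence is that a hold for the morning session is plainly what was meant. The clause belongs to a sentence about a fasted morning session, the readings end at 120 minutes, and nothing tells anyone to stop treatment for a day. That stands in part. A reader might infer that the hold has no timing at all, and the text does not support this. What is missing is the last-dose time and the resumption time.

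A reader might also infer that participants with T1D are ordered off all insulin. That is only the literal reading. The documents do not show that it was intended or that it would be followed.

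Next, the kit instructions, the emails and the consent text may give dose-by-dose advice and values for calling. They are not in the documents, so it would be wrong to say that participants receive no such guidance. The point is confined to the protocol text.

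There are real safeguards: HbA1c of 6.5–8.5%, diabetes for at least a year, a health screening questionnaire before the kit is sent, seven self-readings, familiarity with finger pricks, telephone contact, and freedom to withdraw. They narrow the risk, but none says which doses to keep or when to act.

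Finally, the sentence expecting no adverse events concerns the interventions, meaning the bars, and stands under diet compliance. Its silence therefore does not show that the risk was overlooked. It shows only that the protocol's risk text does not cover the hold.

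**Conclusion.** The point holds as a participant-safety gap in the protocol text: one undifferentiated hold for T1D and T2D in unsupervised fasted sessions, without scope, last-dose time, resumption time or action values, and with no mention in the risk text. It concerns 10 of 20 planned participants most directly.

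No risk figure is claimed, because the documents give no event rate, insulin regimens or carbohydrate content of the bars. A reader might infer that the hold by itself distorts the comparison of the bars. The documents give no data to size that, and randomised bar order means uneven application of the hold would mainly add noise. The result-related issue that does need handling is selective stopping after the conventional bar.

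The conclusion assumes that the protocol's wording is what staff and participants would follow. If the kit or consent text already settles the doses and values, the gap reduces to bringing that text into the protocol.

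**What to change.** 1. Replace the phrase in Research Method with clinician-approved, separate T1D and T2D instructions. Limit the hold to named morning or mealtime doses, keep basal insulin unless the clinician says otherwise, give the resumption time, and set glucose values for not starting, stopping, treating and calling. If the kit instructions already contain this, copy them in.
2. Repeat these instructions in the Day 1 and Day 2 checklists, with a study telephone contact.
3. Extend the risk text under Potential Problems and Alternative Strategies to cover the hold, and record adverse events.
4. In Statistical Analysis, state that readings taken before any stop remain in the mixed model. Require stopped sessions to be reported by bar, and interpret the paired AUC tests with that count in view.

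The cost is a short ethics amendment with clinician sign-off, revised checklists, and possibly a few incomplete pairs, with the 3–10% loss in detectable difference shown above for 1 to 3 lost pairs.
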